1.2 Study objectives and endpoints

Table 1.2-1: Objectives and endpoints

Objective	Endpoint
Primary objective	
To demonstrate that the efficacy of secukinumab 300 mg at Week 16 is superior to placebo in adult patients with active PsA based on the proportion of patients achieving an American College of Rheumatology 20 (ACR20) response.	ACR20 response (yes, no)
Secondary objectives	

To evaluate the efficacy of secukinumab 150 mg compared to placebo at Week 16 in patients with active PsA based on the proportion of patients achieving an American College of Rheumatology 20 (ACR20) response.	ACR20 response (yes, no)
To evaluate the efficacy of secukinumab	Dactylitis (yes no)
300 mg and 150 mg compared to placebo at	
Week 16 based on the proportion of patients	
withdactylitis in the subset of nations who	
have dactylitis at baseline.	
To evaluate the efficacy of secukinumab	Enthesitis (yes, no)
300 mg and 150 mg compared to	
placebo at Week 16 based on the proportion	
of patients with enthesitis in the subset of	
patients who have enthesitis at baseline.	
To evaluate the efficacy of secukinumab	ACR20, ACR50, and ACR70 responses
300 mg and 150 mg compared to	
placebo at Week 16 in subset of patients	
with active PsA and number of tender and	
swollen joints less than 10 at baseline based	
on the proportion of patients achieving	
ACR20, ACR50, and ACR70 responses.	
To evaluate the efficacy of secukinumab	ACR50 and ACR70 responses
300 mg and 150 mg compared to placebo at	
Week 16 based on the proportion of patients	
achieving ACR50 and ACR70 responses.	
To evaluate the efficacy of secukinumab	Minimal Disease Activity (yes, no) (5 of the
300 mg and 150 mg compared to placebo at	following 7 criteria: ≤ 1 tender joint, ≤ 1
Week 16 based on the proportion of patients	swollen joint, PASI ≤ 1 or IGA mod 2011 ≤ 1 ,
achieving Minimal Disease Activity (5 of	patient assessment of pain (0-100 Visual
the following 7 criteria:	Analog Scale (VAS)) ≤ 15 , patient global
≤ 1 tender joint, ≤ 1 swollen joint, PASI ≤ 1 or	assessment of disease (VAS) ≤20, HAQ-DI
IGA mod 2011 ≤ 1 ,, patient assessment of	≤ 0.5 , tender entheseal points ≤ 1)
pain (0-100 Visual Analog Scale (VAS))	
\leq 15, patient global assessment of disease	
$(VAS) \leq 20$, HAQ-DI ≤ 0.5 , tender entheseal	
points ≤1)	
To evaluate the efficacy of secukinumab	PASI75, PASI90, PASI100 responses (yes,
300 mg and 150 mg compared to	no)
placebo at Week 16 based on the proportion	
of patients achieving a PASI75, PASI90,	
and PASI100 responses	

To evaluate the efficacy of secukinumab 300 mg and 150 mg compared to placebo at Week 16 based on the change from baseline in	Change from baseline in DAS28-CRP
DAS28-CRP.	
To evaluate the efficacy of secukinumab 300 mg and 150 mg compared to placebo at Week 16 based on the change from baseline in Psoriatic Arthritis Disease Activity Score (PASDAS).	Change from baseline in Psoriatic Arthritis Disease Activity Score (PASDAS)
To evaluate the efficacy of secukinumab 300 mg and 150 mg compared to placebo at Week 16 based on the change from baseline in SF12.	Change from baseline in SF12
To evaluate the efficacy of secukinumab 300 mg and 150 mg compared to placebo at Week 16 based on the change from baseline in HAQDI.	Change from baseline in HAQ-DI
To evaluate the overall safety and tolerability of secukinumab 300 mg and 150 mg compared with placebo as assessed by vital signs, clinical laboratory values, and adverse events (AE) monitoring.	Overall safety, as measured by frequency and severity of adverse events (AE) monitoring and changes in clinical laboratory values and vital signs from baseline

2 Statistical methods

2.1 Data analysis general information

Data will be analyzed by Novartis Product Life-Cycle Services and/or a designated Contract Research Organization.

It is planned that the data from all centers that participate in this protocol will be combined, so that an adequate number of patients will be available for analysis. Analysis datasets and statistical outputs will be produced using the most recent SAS[®] Version 9.4 (SAS Institute Inc., Cary, NC, USA), and stored in Novartis global programming & statistical environment (GPS).

As the primary analysis time point is Week 16, there will be a database lock after all patients have completed the Week 16 visit and data are clean and complete. At that time, only the statistician and programmer(s) from Novartis and/or a designated CRO will be unblinded in order to perform the analysis. Results from the analyses of all data through Week 16 will be shared internally. For publication purposes, summary results from the Week 16 primary analysis time point may be shared with the health care community; however, individual subject-level data will remain blinded until the end of the trial. A final database lock will occur when all patients have completed the study.

Summary statistics for continuous variables will include mean, standard deviation, standard error of mean, median, 25th and 75th percentiles, interquartile range, minimum, and maximum at each time point. Summary statistics for discrete variables will be presented in the number and percent of patients in each category. Summary statistics will also be presented graphically wherever applicable. If not otherwise specified, p-values and confidence interval (CI) will be presented as two-sided and the default level of significance will be set to 0.05 (two-sided). For all continuous variables (efficacy and safety), change from baseline and percentage change from baseline by visit will also be presented.

Data analyses will be presented by treatment group. Efficacy and safety data for the placebocontrolled period (or the entire Treatment Period as appropriate) will be presented by the following 3 treatment groups. Patients may be included in more than one treatment group for some analyses (e.g. exposure-adjusted adverse events over the entire treatment period).

Eligible patients will be randomized to secukinumab 300 mg (Group 1), secukinumab 150 mg (Group 2) or placebo (Group 3) for the first 16 weeks (until Week 16 treatment). Note that the treatment groups above for a patient may differ depending on the time period of the analysis and whether one assesses the patient for efficacy or safety.

The analysis will be conducted on all patients' data at Week 16 and at the time the trial ends (Week 52).

For Treatment Period 2, all data analyses will be presented by Weeks 16, 28 and 40, based on the number of patients who switched to secukinumab 300 mg and number of patients who continued in secukinumab 150 mg at the respective visits.

All the assessments from scheduled visits will be included for summaries and analyses, whereas the listing will include available data.

Comparative efficacy data

Comparative efficacy analyses (i.e. inferential efficacy comparisons with placebo) will focus on the time period when both active drug and the placebo are given in a manner suitable for making comparisons (i.e., first 16 weeks of treatment). Comparative efficacy will be performed based on the FAS using the randomized treatment. After week 16 till week 52, the efficacy variables will be summarized descriptively or otherwise specified using inferential analysis, on the FAS.

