3.6 Risks and benefits

Secukinumab has shown confirmed efficacy in several inflammatory diseases and approved by the EMA and FDA for the treatment of active PsA and AS in adult patients. The safety profile of secukinumab is primarily based on the aggregate safety data from 10 large completed phase II/III psoriasis trials. The evaluation of safety data from completed PsA trials did not show additional safety concerns.

Secukinumab was generally safe and well-tolerated. The most frequently reported adverse events (AE) are infections, especially upper respiratory tract with secukinumab relative to placebo. There was an increase in mucosal or cutaneous candidiasis with secukinumab compared to placebo, but the cases were generally mild or moderate in severity, non-serious, and responsive to standard treatment.

There was a small increase in mild neutropenia cases with secukinumab compared to placebo. Common Toxicity Criteria (CTC) AE grade 3 neutropenia ($<1.0-0.5 \times 10^9/L$) was uncommonly observed with secukinumab, most were transient and reversible without a temporal relationship to serious infections.

Hypersensitivity reactions include urticarial and rare event of anaphylactic reaction to secukinumab were also observed in clinical studies.

Taking into account the individual risks as outlined above, the expected risk profile of secukinumab from a mechanism of action perspective is anticipated to be similar or improved compared to the approved inflammatory cytokine-targeting therapies. The risk to patients in this trial will be minimized by compliance with the eligibility criteria, close clinical monitoring and extensive guidance to the investigators, provided in the current version of the IB. The completed FUTURE 1 and 2 trials confirmed the significant clinical benefits to secukinumab treatment in PsA patients observed as early as 1-3 weeks in all PsA related joint, skin and other symptoms such as dactylitis and enthesitis.

From the standpoint of the overall risk-benefit assessment, current trial with secukinumab is justified.

4 Population

The study population will be comprised of the following patients who have passed screening assessments, comply with eligibility criteria and have provided written consent:

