For patients who discontinue study treatment prematurely for any reason before the end of **Treatment Period 1**, (Visit 10/Week 16 EOT1) must be performed approximately four weeks after the last dose of study treatment (secukinumab 300 mg, secukinumab 150 mg or placebo). Patients should also be contacted via telephone, 84 days (12 weeks) after last dose of study drug, to inquire about any AE/SAEs that occurred during this period.

For patients who discontinue study treatment prematurely for any reason before the end of **Treatment Period 2**, (Visit 19/ Last visit EOT2) must be performed approximately four weeks after the last dose of study treatment (300 mg or 150 mg s.c. secukinumab). Patients should also be contacted via telephone, 84 days (12 weeks) after last dose of study drug, to inquire about any AE/SAEs that occurred during this period.

If patients refuse to return for these assessments or are unable to do so, every effort should be made to contact them or a knowledgeable informant by telephone to determine the reason.

At a minimum, patients will be contacted for safety evaluations during the 84 days (12 weeks) following the last study visit or following the last administration of study treatment (whichever is later), including a final contact at the 84-day point. Documentation of attempts to contact the subject should be recorded in the source documentation.

AE/SAE information obtained as a result of these calls must be recorded in the eCRF.

Unscheduled visits

Patients may be seen at any time for an unscheduled visit, e.g., if they experience deterioration or AEs that in the opinion of the investigator/qualified site staff need intervention or repeat laboratory testing. The assessment(s) performed at an unscheduled visit must include at minimum: an assessment of concomitant medication and procedures/significant non-drug therapies, vital signs, and an AE/SAE assessment. Any additional assessments performed are at the investigator/qualified site staff's discretion. During an unscheduled visit, study treatment will not be administered.

Table 6-1 Assessment schedule

Period	SCR ¹		Treatment Period 1								Treatment Period 2									Unscheduled Visit	
Week	-8 to BL		BL	1	2	3	4	8	12	16/EOT	20	24	28	32	36	40	44	48	52/EOT		Day 84 Safety Follow-up ⁴
Visit No	1	2	3	4	5	6	7	8	9	10	11	12	13	14	15	16	17	18	19		
Visit Window (days) ²				+/-2	+/-2	+/-2	+/-2	+/-2	+/-2	+/-2	+/-7	+/-7	+/-7	+/-7	+/-7	+/-7	+/-7	+/-7	+/-7		
Assessments																					

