2.1.2 Visits windows

Visit-windows will be used for the data that is summarized by visit; they are based on the study evaluation schedule and comprise a set of days around the nominal visit day. For any assessment, there are the protocol defined scheduled visits around which visit windows were created to cover the complete range of days within the study. The visit windows are shown in Table 2-1. These apply to measurements taken at every visit. For assessments collected less often, different visit windows will be applied as detailed below.

When visit windows are used, all visits will be re-aligned, i.e., they will be mapped into one of the visit windows. For example, if the *Week 4* visit of a subject is delayed and occurs on Day 46 instead of on Day 29, say, it will be re-aligned to visit window *Week 8*. In the case of major deviations from the visit schedule, or due to unscheduled visits, several assessments of a subject

may fall in a particular visit window (either scheduled or unscheduled). Statistical approaches to handle multiple assessments in a given visit window are specified below.

Of note, subjects are allowed to have gaps in visits.

Analysis Visit	Week	Scheduled Day	Visit Window
Baseline	BSL	1	-28 days to Day 1*
Week 1	1	8	Day 2-11
Week 2	2	15	Day 12-18
Week 3	3	22	Day 19-25
Week 4	4	29	Day 26-43
Week 8	8	57	Day 44-71
Week 12	12	85	Day 72-99
Week 16	16	113	Day 100-127
Week 20	20	141	Day 128-155
Week 24	24	169	Day 156-183
Week 28	28	197	Day 184-211
Week 32	32	225	Day 212-239
Week 36	36	253	Day 240-267
Week 40	40	281	Day 268-295
Week 44	44	309	Day 296-323
Week 48	48	337	Day 324-351
Week 52	52	365	Day 352-379

Table 2-1Assessment windows for scheduled visits

* Baseline measurement before the first drug administration for safety assessments and before the randomization for efficacy assessments. For efficacy, visit windows refer to date of randomization.

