2.1.3 Multiple assessments within visit windows

When there are *multiple assessments* in a particular visit window, the following rules are applied to select one value "representing" the subject in summary statistics in a visit window (See Table 2-2).

For baseline assessment definition, see section 2.1.1. For post-baseline visit windows, the following applies (unless otherwise specified):

- for *quantitative variables*, the *closest* to the actual visit is chosen (if two assessments have the same distance, then the earlier one will be chosen);
- for *qualitative variables*, the *worst* record is selected. It is noted that in the analyses performed, *worst* case is always well defined.
- in case qualitative variables are based on quantitative variables, e.g., PASI 75 response, the visit will be assigned to the quantitative variable, and this visit will be used for the derived qualitative variable.

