Decreased Lymphocyte	<lln -="" 1.5="" 10e9="" l<="" td="" x=""><1.5 - 1.0 x 10e9 /L	<1.0 - 0.5 x 10e9 /L	<0.5 x 10e9 /L	</lln>	<1.5 - 1.0 x 10e9 /L	<1.0 - 0.5 x 10e9 /L	<0.5 x 10e9 /L
count Decreased	<lln -="" 0.8="" 10e9="" l<="" td="" x=""><0.8 - 0.5 x 10e9 /L	<0.5 - 0.2 x 10e9 /L	<0.2 x 10e9 /L	</lln>	<0.8 - 0.5 x 10e9 /L	<0.5 - 0.2 x 10e9 /L	<0.2 x 10e9 /L
Creatinine increased*	>1 - 1.5 x baseline; >ULN - 1.5 x ULN	>1.5 - 3.0 x baseline; >1.5 - 3.0 xULN	>3.0 baseline; >3.0 - 6.0 x ULN	>6.0 x ULN
TBL increased	>ULN - 1.5 x ULN	>1.5 - 3.0 x ULN	>3.0 - 10.0 x ULN	>10.0 x ULN
GGT increased	>ULN - 2.5 x ULN	>2.5 - 5.0 x ULN	>5.0 - 20.0 x ULN	>20.0 x ULN
ALT increased	>ULN - 3.0 x ULN	>3.0 - 5.0 x ULN	>5.0 - 20.0 x ULN	>20.0 x ULN
AST increased	>ULN - 3.0 x ULN	>3.0 - 5.0 x ULN	>5.0 - 20.0 x ULN	>20.0 x ULN
ALP increased	>ULN - 2.5 x ULN	>2.5 - 5.0 x ULN	>5.0 - 20.0 x ULN	>20.0 x ULN

Table 2.8-2CTCAE grades for laboratory variables to be analyzed

Glucose increased				
(Hyperglycemia				
)	>ULN - 8.9 mmol/L	>8.9 - 13.9 mmol/L	>13.9 - 27.8 mmol/L	>27.8 mmol/L
Glucose				
decreased				
(Hypoglycemia)	<lln -="" 3.0="" l<="" mmol="" td=""><3.0 - 2.2 mmol/L	<2.2 - 1.7 mmol/L	<1.7 mmol/L	</lln>	<3.0 - 2.2 mmol/L	<2.2 - 1.7 mmol/L	<1.7 mmol/L
		>7.75 - 10.34		
Cholesterol high	>ULN - 7.75 mmol/L	mmol/L	>10.34 - 12.92 mmol/L	>12.92 mmol/L
Hypertriglycerid				
emia	1.71 - 3.42 mmol/L	>3.42 - 5.7mmol/L	>5.7 - 11.4 mmol/L	>11.4 mmol/L
*NT-4 C		1	1	

*Note: for "creatinine increased" the baseline criteria do not apply

Shift tables will be presented comparing baseline laboratory result (CTCAE grade) with the worst results (expressed in CTCAE grade) during the treatment phase (either initial or entire) analyzed. Of note, baseline will be defined as last assessment prior to first dosing in initial treatment phase. Patients with abnormal laboratory values will be listed and values outside the normal ranges will be flagged.

Newly occurring or worsening liver enzyme abnormalities will also be summarized based on the event criteria given in Table 2.8-3 below:

Parameter	Criterion
ALT	>3xULN; >5xULN; >8xULN;>10xULN, >20xULN
AST	>3xULN; >5xULN; >8xULN >10xULN; >20xULN
ALT or AST	>3xULN; >5xULN; >8xULN >10xULN; >20xULN
TBL	>1.5xULN, >2xULN, >3xULN,
ALP	>2xULN, >3xULN. >5xULN
ALT or AST &	ALT or AST>3xULN & TBL >2xULN;
TBL	ALT or AST >5xULN & TBL >2xULN;
	ALT or AST >8xULN & TBL >2xULN;

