	ALT or AST >10xULN & TBL >2xULN
ALP & TBL	ALP >3xULN & TBL >2xULN
	ALP >5xULN & TBL >2Xuln
ALT or AST &	ALT or AST>3xULN & TBL >2xULN & ALP <2xULN (Hy's Law)
TBL & ALP	Note: elevated ALP may suggest obstruction as a consequence of gall
	bladder or bile duct disease; ALP may also be increased in
	malignancy. FDA therefore terms Hy's Law cases as indicators of
	pure hepatocellular injury. This does not mean that cases of ALT or
	AST >3xULN & TBL >2xULN & ALP ≥2xULN may not result
	in severe DILI.

Table 2.8-3Liver-related events

Notes:

In studies which enroll patients with pre-existing liver disease, baseline LFT may be increased above ULN; in such a case it is meaningful to add the condition "and worse than baseline" to the abnormality Criteria

For a combined criterion to be fulfilled, all conditions have to be fulfilled on the same visit. The criteria are not mutually exclusive, e.g. a subject with ALT = 6.42xULN is counted for ALT > 3xULN and ALT > 5x ULN.

Novartis	For business use only	Page 34
SAP		Secukinumab/AIN457FUS01

Individual subject data listings will be provided for patients with abnormal laboratory data. Data of patients with newly occurring or worsening liver enzyme abnormalities will be listed in an additional listing.

Separate summaries and listings will be provided for urine pregnancy results by visit for each treatment period.

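### SAP 2.1, read naturally, keeps unscheduled values out of summaries, which conflicts with 2.1.2 and leaves the worst-value safety tables without a stated data source

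*SAP*

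**What the plan says.** - **SAP 2.1 (general rule).** "All the assessments from scheduled visits will be included for summaries and analyses, whereas the listing will include available data". The section covers efficacy and safety alike.
- **SAP 2.1.2 (visit windows).** "When visit windows are used, all visits will be re-aligned, i.e., they will be mapped into one of the visit windows". It adds that several assessments of one patient "may fall in a particular visit window (either scheduled or unscheduled"). The windows are meant for data summarised by visit.
- **SAP 2.1.3 (more than one value in a window).** For quantitative variables the value closest to the visit represents the patient; for qualitative variables the worst record does. For mixed cases, "in case qualitative variables are based on quantitative variables, e.g., PASI 75 response, the visit will be assigned to the quantitative variable", and the derived category follows that choice. These rules hold unless otherwise specified.
- **SAP 2.8.3 (laboratory).** It asks for the maximum change per study period, the shift to the most extreme value per treatment period, and a shift table against the "worst results (expressed in CTCAE grade) during the treatment phase". It also asks for liver events including Hy's Law, with the note: "For a combined criterion to be fulfilled, all conditions have to be fulfilled on the same visit".
- **SAP 2.8.4.2 (vital signs).** It counts patients with newly occurring notable values.
- **Protocol Section 6, Unscheduled visits.** Patients may be seen at any time, for example "if they experience deterioration or AEs that in the opinion of the investigator/qualified site staff need intervention or repeat laboratory testing". Vital signs are part of the minimum content of such a visit.

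**The concern.** The word 'whereas' in SAP 2.1 does some work only if listings hold data that the summaries do not. The obvious candidates are values from unscheduled visits. Those visits happen because a patient has deteriorated or has an adverse event, so they are a likely place for extreme values. Protocol 6.5.5 adds to them by requiring clinically significant abnormal results to be followed until they return to normal or are explained.

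The outputs in SAP 2.8.3 and 2.8.4.2 depend on extremes. Neither section says whether unscheduled values count, and neither lifts the general sentence. Two programmers could follow this SAP faithfully and report different numbers of grade 3 to 4 cytopenias or Hy's Law cases.

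Safety judged by laboratory values and vital signs is a stated secondary objective. Neutropenia is a named risk. Protocol 3.6 describes grade 3 cases as uncommon and says that "most were transient and reversible without a temporal relationship to serious infections". When events are few and short, the handling of a single value can change a table.

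**Working it through.** The plan gives no figure on this point to reproduce. The check compares the texts and adds two short calculations.

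**1. One value, three readings.** Take a laboratory value drawn at an unscheduled visit because of an adverse event.

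| Rule taken to govern | Listing | Worst-grade, most-extreme and liver-event tables |
|---|---|---|
| SAP 2.1, natural reading | yes | no |
| SAP 2.1.2 and 2.1.3, applied before extremes are taken | yes | only if it is the value selected in its window |
| SAP 2.8.3, read as all values in the period | yes | yes |

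The SAP does not say which row applies. The Hy's Law note requires the same visit but does not limit visits to scheduled ones, so it does not settle the matter. For notable vital signs, 2.8.4.2 gives no period-level wording and no data source.

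**2. Do the windows take in unscheduled values?** SAP Table 2-1 has 16 post-baseline windows, from Day 2-11 (Week 1) to Day 352-379 (Week 52). Each starts the day after the one before it ends, so they cover 379 − 2 + 1 = 378 days without a gap. Under 2.1.2, any post-baseline value in that range therefore falls in a window. This is a direct conflict with the natural reading of 2.1.

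**3. When could the closest-value rule remove an unscheduled extreme?** Protocol Table 6-1 allows ±2 days at 7 visits (Weeks 1 to 16) and ±7 days at 9 visits (Weeks 20 to 52).

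- Days inside a protocol visit window: 7 × 5 + 9 × 15 = 35 + 135 = 170.
- Days inside an analysis window but outside every protocol visit window: 378 − 170 = 208, and 208/378 = 55%.

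On those 208 days, an unscheduled value is farther from the nominal day than any on-time scheduled value in the same window. If both are present and 2.1.3 is applied first, the unscheduled value loses. A laboratory grade is a category derived from a quantity, so it would follow that choice.

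The 55% is a share of calendar days, not a probability of loss. Hematology and chemistry are drawn at only some visits, so many Table 2-1 windows would hold no scheduled laboratory value to compete. SAP 2.1.2 also promises other windows for assessments collected less often, and the text available for review does not show them.

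**4. Direction.** Let S be a patient's scheduled post-baseline values and A all post-baseline values, so S is contained in A. The worst value over S cannot be more extreme than the worst over A. A combined criterion met at some visit in S is also met in A. With baseline held fixed, leaving out unscheduled values can therefore reduce the number of patients at or beyond a threshold, or leave it unchanged, but cannot increase it.

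**5. Size.** This would need the number of unscheduled values and how often one is the patient's worst. Neither is in the documents, so no undercount can be calculated.

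**The case against.** The strongest reply is that the SAP, read as a whole, already admits unscheduled values. SAP 2.1 never says 'only'. The more specific 2.1.2 names unscheduled assessments, and 2.1.3 provides for choosing among them, which would have little purpose if they were excluded. The 2.1.3 selection serves summary statistics within a visit window and yields where something else is specified. SAP 2.8.3 arguably does specify something else, because it asks for extremes over a whole period.

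Much of this stands. A reader might infer that unscheduled values are certain to be lost, or that 2.1.3 throws away peaks and nadirs. The documents do not support either as a settled fact. Both are possible readings of a text that conflicts with itself, and for 2.1.3 the period-level reading of 2.8.3 is the more natural one.

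The reply does not close the gap. The windows in 2.1.2 serve by-visit data, so they do not clearly override the general sentence for period-level tables. 'Unless otherwise specified' helps only if 2.8.3 specifies which values are used, and it does not. SAP 2.8.4.2 lacks even the period wording.

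Other routes to detection also exist. Under Protocol 7.1, laboratory abnormalities that are clinically significant, cause symptoms or need treatment are adverse events, and these are tabulated under SAP 2.8.1. Abnormal values are listed, with an additional listing for liver abnormalities. These lessen the consequence, but they do not make the grade, liver-event and notable-value tables well defined.

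**Conclusion.** SAP 2.1 conflicts with 2.1.2, and the sections that produce worst-value and threshold counts do not say which rule governs. If 2.1 is followed, the missed values come from visits prompted by clinical problems, and the error runs in one direction: counts too low or unchanged. This rests on reading 'whereas' in its ordinary sense, on unscheduled values being collected as Protocol Section 6 provides, and on baseline staying the same. The possible loss through 2.1.3 is a secondary gap that depends on the order of the programming steps.

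The size is unknown. A reader might try to infer it from how seldom laboratory draws are scheduled. That would give the chance that a scheduled draw coincides with a short episode, not the number of values lost through 2.1. An episode that no scheduled draw catches yields an unscheduled value only if something prompts a visit; otherwise no value exists for any SAP wording to recover. Vital signs are scheduled at nearly every visit, so such reasoning would not carry over to them.

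Nothing here shows an effect on the efficacy conclusions or a bias between arms, and tables need not disagree with listings that are meant to be broader. The point should still be corrected: safety is a stated objective and the repair is small.

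**What to change.** 1. In SAP 2.1, limit the scheduled-visit sentence to by-visit summaries and reconcile it with 2.1.2, so that one rule states how unscheduled values enter the windows.
2. Add to 2.8.3 and 2.8.4.2 a sentence such as: *Worst CTCAE grade, maximum change, most extreme value, liver-event and notable-value summaries use all post-baseline values in the analysis period, scheduled and unscheduled; the closest-to-visit rule in 2.1.3 does not apply to them.*

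The cost is a few sentences and a dataset flag marking the records used for period-level extremes. The downside is that abnormality counts may be slightly higher. The SAP's revision history records updates after the Week 16 database lock. If Week 16 safety tables already exist, the report should state which rule they used and whether they were rerun.
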